10.3. Permitted Concomitant Therapy

This section should be consistent with the medication restrictions in the inclusion/exclusion criteria previously listed. Describe how allowed concomitant therapy might affect the outcome (e.g., drug-drug interaction, direct effects on the study endpoints).

N/A

10.4. Rescue Medicine

List all medications, treatments, and/or procedures that may be provided during the study for “rescue therapy” and relevant instructions.

N/A, no rescue medicine

11. Study Intervention Discontinuation

11.1. Discontinuation of Study Intervention

Describe the criteria for discontinuing the study intervention (e.g., halting rules), including any monitoring test(s) and associated clinical decision point(s). Include reasons for temporary discontinuation of the study intervention (e.g., type and quantity of adverse events), clearly stating the length of time, if applicable, and describe the data to be collected at the time of study intervention discontinuation and approaches for restarting administration of or re-challenging with study intervention.

Study will be discontinued if more than 5% of subjects present an adverse reaction such as infection or material recall. Such a reaction would be extremely rare as the study material is FDA approved and in the US market since 2016.

11.2. Continued Follow-up Discontinuation of Study Intervention

Describe efforts that will be made to continue follow-up of participants who discontinue the study intervention, but remain in the study for follow-up, especially for safety and efficacy study endpoints (if applicable). Reasonable efforts must be made to undertake protocol-specified safety follow-up procedures to capture adverse events (AE), serious adverse events (SAE), and unanticipated problems involving risks to subjects or others (UPIRSOs).

All patients that participate in the study, including those discontinued due to adverse reactions, will be followed until completion of the study or resolution of the adverse reaction (unless consent has been withdrawn).

12. Statistical Considerations

12.1. Statistical Hypotheses

State the formal and testable null and alternative hypotheses for primary and key secondary endpoints, specifying the type of comparison (e.g., superiority, equivalence or non-inferiority, dose response) and time period for which each endpoint will be analyzed.

Hypotheses: a.) No difference in % vital bone, % residual graft and % connective /other tissues between BioOss Collagen and Ossix Bone groups. b.) No dimensional differences in alveolar ridge after ridge preservation with BioOss Collagen or Ossix Bone.

12.2. Sample Size Determination

Include number of participants to recruit, screen, and enroll to have adequate power to test the key hypotheses for the study. Provide all information needed to validate your calculations and judge the feasibility of enrolling and following the necessary number of participants.

Power analysis revealed a sample size of 14 patients per group was enough to detect a mean difference in percentage of new bone formation of 1 SD by Mann-Whitney U test at the 0.05 level with a power of 88.5%. Anticipating a potential 30% dropout rate and needing 14 fully compliant patient per treatment group, 22 patients will be enrolled in each group.

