12.3. Populations for Analyses

Clearly identify and describe the analysis datasets (e.g., which participants will be included in each).

All study participants who complete the study intervention will be included in the analysis for all outcome measures.

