12.4. Statistical Analyses

Include analysis of primary efficacy endpoints, secondary endpoints, safety analyses, and any planned interim analyses

The outcomes of the histologic and clinical parameters will be summarized with the sample size, mean, standard deviation, median, minimum and maximum. The significance of variation in the mean with group BioOss collagen or Ossix Bone will be assessed with two-sample *t*-testing. The significance of variation in the group effect with another variable will be assessed with an interaction term in a linear model. All statistical testing will be two-sided with a significance level of 5%. Spearman rank and Pearson correlations between clinical parameters and histologic parameters will be analyzed as well. All statistical analyses will be done with statistical software.

References:

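### The 88.5% power in 12.2 is for a Mann-Whitney test with no stated distribution; the two-sided t-test planned in 12.4 has about 72% power at 14 per group under normality

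*Combined protocol and SAP*

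**What the plan says.** Section 12.2 contains the whole sample size argument. It puts the requirement at 14 patients per group, for this target: "mean difference in percentage of new bone formation of 1 SD by Mann-Whitney U test at the 0.05 level with a power of 88.5"%. On enrolment it says: "Anticipating a potential 30% dropout rate and needing 14 fully compliant patient per treatment group, 22 patients will be enrolled in each group". The section gives no distribution for the bone percentages, no sidedness, and no method or software. The template prompt under the same heading asks authors to "Provide all information needed to validate your calculations and judge the feasibility of enrolling and following the necessary number of participants".

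Section 12.3 defines who is analysed: "All study participants who complete the study intervention will be included in the analysis for all outcome measures".

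Section 12.4 defines the test: "The significance of variation in the mean with group BioOss collagen or Ossix Bone will be assessed with two-sample" (the sentence ends by naming the t-test). It adds: "All statistical testing will be two-sided with a significance level of 5"%. Mann-Whitney does not appear in 12.4.

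**The concern.** The test that was powered is not the test that will be used. Mann-Whitney power for a shift of 1 SD depends on the shape of the data, so 88.5% cannot be checked without a stated distribution. It also looks too high: under normality Mann-Whitney is slightly less efficient than the t-test, and a t-test with 14 per group and a 1 SD difference falls well short of 88.5%.

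Two things are at stake. First, this figure is the only support for the sample size. Second, the hypotheses in 12.1 are stated as no difference between the materials. A non-significant result could be read as similarity on the strength of a high stated power that the planned analysis does not have.

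**Working it through.** **Inputs.** Difference 1 SD (d = 1), 14 per group, 0.05 level, stated power 88.5%, 30% dropout and 22 enrolled per group (12.2); two-sample t-test, two-sided 5% (12.4).

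**Step 1: reproduce the plan's figure.** A common approximation gives Mann-Whitney power as t-test power at n × ARE per group, where ARE is the asymptotic relative efficiency of Mann-Whitney to the t-test for the assumed distribution.
- Normal, ARE = 3/π = 0.955: effective n = 14 × 0.955 = 13.4, power 70.0%.
- Logistic, ARE = π²/9 = 1.097: effective n = 15.4, power 76.3%.
- Laplace, ARE = 1.5: effective n = 21, power 88.53%. This matches the stated figure.

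So 88.5% can be reproduced with a two-sided test and a Laplace distribution, neither of which 12.2 states. One-sided testing under normality does not reach it: 80.8% for Mann-Whitney by the same formula and 82.4% for the t-test.

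**Step 2: power of the planned test.** Under normality, two-sided t-test power comes from the noncentral t with 2n − 2 degrees of freedom and noncentrality d√(n/2). At n = 14 that is 26 degrees of freedom and noncentrality √7 = 2.646.

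| Evaluable per group | t-test power, d = 1 |
|---|---|
| 14 | 72.1% |
| 15 | 75.3% |
| 17 | 80.7% |
| 21 | 88.5% |
| 22 | 90.0% |

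At 14 per group the t-test has 80% power for a difference of 1.10 SD and 88.5% power for 1.24 SD.

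**Step 3: does another distribution rescue the figure?** Simulated two-sided 5% power at 14 per group for a 1 SD shift (200,000 runs per shape). The Mann-Whitney range runs from the continuity-corrected to the exact version.

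| Shape | t-test | Mann-Whitney |
|---|---|---|
| Uniform | 71.7% | 63.2–65.2% |
| Normal | 72.3% | 68.1–69.9% |
| Logistic | 72.7% | 72.4–74.1% |
| Gamma, shape 4 | 72.9% | 74.4–76.1% |
| t, 5 df | 74.1% | 77.0–78.6% |
| Laplace | 73.3% | 78.9–80.5% |
| Exponential | 74.1% | 85.8–86.9% |
| t, 3 df | 79.3% | 88.8–89.8% |

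The formula is optimistic at this size: it gives 88.5% for Laplace data, but simulation gives about 80%. Within this set Mann-Whitney comes near 88.5% only for the exponential and the t with 3 df. The planned t-test stays between 72% and 79% throughout.

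**Step 4: link to enrolment.** 14/(1 − 0.30) = 20, so 22 is slightly more than 30% dropout requires. At 30% dropout, 22 × 0.70 = 15.4 remain, where t-test power is about 75%. Reaching 80% needs 17 evaluable per group, so at most 5 of 22 lost (5/22 = 22.7%), fewer than the plan anticipates.

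**The case against.** **The stated figure is not an arithmetic slip.** This stands. It reproduces under a Laplace assumption, so the defect is an undisclosed assumption together with a mismatch between the powered and the planned test. Mann-Whitney under normality at 22 per group also gives 88.5%, but only because 22 × 3/π and 14 × 1.5 both equal about 21. That coincidence is no evidence of how the figure was obtained.

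**The simulated ranges depend on the shapes chosen.** This also stands. A lognormal with sigma 1 takes the t-test to 81%. A t distribution with 2.5 df takes it to about 85%, and one with 2.2 df to about 93%. A lognormal can also carry Mann-Whitney past 88.5% (84.0% at sigma 0.5, 97.3% at sigma 1). The documents give no reason to expect such tails in a percentage bounded by 0 and 100. For three bounded beta shapes, t-test power was about 72%.

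**Fourteen is a floor, not the expected number.** This is partly right. If all 22 were evaluable, power would be 90%, above the stated figure. But 12.2 ties its claim to 14, and the plan's own dropout rate leaves about 15.

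**The mismatch changes little in conduct.** Type I error is unaffected, 12.4 is clear about the test, no passage commits the trial to 80% power, and the request for full information is a form prompt. All true, but none of it makes 88.5% the power of the planned analysis.

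**Conclusion.** The concern holds: the power statement is wrong as written for the analysis that 12.4 specifies. Assuming normal data, equal groups and a true 1 SD difference, the planned two-sided 5% t-test has 72% power at 14 per group and 75% at 15, against the stated 88.5%. The chance of missing that difference at 14 completers is about 28% (21–28% across the eight shapes simulated), where the plan implies 100 − 88.5 = 11.5%. The stated figure depends on a distribution the plan does not name. Under the Laplace assumption that reproduces it by formula, simulation supports it neither for Mann-Whitney (about 80%) nor for the planned test (about 73%). The t-test figure of 72% is exact under normality; the other shapes are illustrative, since the documents give no data on the distribution of the bone percentages.

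**What to change.** Name the same primary test in 12.2 and 12.4, and state the distribution, sidedness and method behind the power figure. If the t-test is kept, 12.2 could read:

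> With 14 evaluable patients per group, a two-sided 5% two-sample t-test has 72% power for a 1 SD difference in % vital bone, assuming normal data. Power is 75% with 15 per group, about the number expected after 30% dropout, and 90% if all 22 are evaluable. The difference detectable with 80% power at 14 per group is 1.10 SD.

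Add one sentence either saying why power below 80% at 14 completers is accepted, or noting that 80% is reached if at least 17 of 22 per group are evaluable. If Mann-Whitney is preferred, change 12.4 to match and give the assumed distribution, with power checked by simulation at 14 per group rather than taken from the efficiency formula alone.

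The cost is a wording change in two sections. Enrolment and data collection stay as they are. The sponsor has to report and defend a less favourable power: 72% instead of 88.5% at the planned number of completers.

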12.3. Populations for Analyses

Clearly identify and describe the analysis datasets (e.g., which participants will be included in each).

All study participants who complete the study intervention will be included in the analysis for all outcome measures.

12.4. Statistical Analyses

Include analysis of primary efficacy endpoints, secondary endpoints, safety analyses, and any planned interim analyses

The outcomes of the histologic and clinical parameters will be summarized with the sample size, mean, standard deviation, median, minimum and maximum. The significance of variation in the mean with group BioOss collagen or Ossix Bone will be assessed with two-sample *t*-testing. The significance of variation in the group effect with another variable will be assessed with an interaction term in a linear model. All statistical testing will be two-sided with a significance level of 5%. Spearman rank and Pearson correlations between clinical parameters and histologic parameters will be analyzed as well. All statistical analyses will be done with statistical software.

References:

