8.8 Description of Methods (or include in separate document)

Check to indicate that the Methods are described in an attached file →

Each extraction socket will receive one 5 X 5 X 8mm or 5 X 5 X 10mm graft cube (research) with no attempt to fill the entire socket. No wound dressing or membrane will be used to cover the bone graft material as both materials can be used alone. All extraction sockets will be sutured with Vicryl 4.0 mattress suture which will be removed approximately 2 weeks (\pm 1 week) after the procedure as per standard of care. All patients will be prescribed an oral antibiotic after the procedure either Amoxicillin 500mg three times per day for 7 days, or if they are allergic to penicillin/amoxicillin they will be prescribed Clindamycin 300mg three times per day for 7 days as per standard of care.

In keeping with the protocol our study group has used several times before, the plan will be to extract non-molar teeth and graft with the test/control materials. Each subject will provide a single non-molar tooth site for study treatment. Following approx. 14 weeks of healing, we will harvest a core biopsy at the time of implant placement. The core biopsy will then be evaluated for the primary outcomes: % vital bone formation, % residual graft material, and % "CT/other" (fibrous tissue and marrow space). We will also evaluate the following secondary outcomes using a custom measuring stent for each subject: change in ridge width; change in buccal ridge height, and change in lingual ridge height. During the 14-week healing period, subjects will be followed up with biweekly and monthly visits as per standard of care, to evaluate healing.

A detailed visit by visit outline is provided below:

Step-by-Step Methods: All the procedures are routinely performed in the graduate periodontics clinic as part of standard care. The methodology is the same previous studies of our group HSC20130470H, HSC20150708H, HSC20170339H, HSC20170267H, among others.

Visit 1 - Screening examination:

If a patient presents at a consultation appointment at the graduate periodontics clinic with a non-molar tooth (incisors, canines, premolars) that needs to be extracted and replaced with a dental implant, the treating doctor will provide:

- Explanation to the patient of the purposes of the study and the planned procedures related to the study.
- Explanation to the patient of the risks, benefits and possible complications of participation in the study.

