- Notification to the patient that inclusion in the study is voluntary and conditional upon satisfying the inclusion and exclusion criteria.

Patient will be given the opportunity during the appointment to ask any question that he/she may have. Following an informational discussion with the prospective subject, consent will be obtained within 2 weeks. This is up to the discretion of the patient. If the patient would like to become a subject for entry into the study, he or she can do so immediately, or can consider it for up to 2 weeks (must be prior to extraction).

Visit 2 – Extraction with ridge preservation using either 90% bovine derived xenograft granules and 10% porcine collagen (Bio-Oss® Collagen, Geistlich, Inc.) or a resorbable sponge-like matrix of 80% hydroxyapatite and 20% sugar ross-linked porcine collagen (Ossix™ Bone, Datum Dental Ltd).

The patient will be assigned to either group by simple randomization with a 1:1 ratio

If the patient has agreed to participate in the study, informed consent will be obtained and documented on a written consent form. If not, standard care treatment will be provided to the patient, but the patient would not be included in the study.

On the day of the planned extraction, the medical history will be updated.

Pregnant women or women intending to become pregnant during the study period: Prior to dental surgery, females of child-bearing age are asked verbally if there is any possibility that they are pregnant. If not, we proceed with surgery and no pregnancy test is done. If the woman states that there is a possibility that she is pregnant, an over the counter urine pregnancy test to rule pregnancy in or out will be provided. Use of the urine pregnancy test is only done if she says she may be pregnant. [If needed: Urine pregnancy test will be provided to female subjects in the graduate periodontics clinic of UTHSCSA and a negative result is required to enter the study.]

Impressions of the arch with the tooth to be extracted in place will be taken prior to extraction and poured in stone to obtain initial study casts (research). If the tooth to be extracted is fractured, a wax-up of the tooth will be made before the stent is fabricated (research).

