One measurement stent will be fabricated to facilitate clinical ridge measurements. A clear suck-down resin measuring stent will be fabricated in the laboratory to allow standardization of the location of clinical measurements of ridge width and height through small holes that will be placed in the stent at the time of tooth extraction.

The width of keratinized tissue will be recorded clinically to the nearest 0.5mm using a periodontal probe at the mid-buccal and mid-lingual sites of the tooth to be extracted.

A pre-operative periapical radiographic image will be taken before the extraction as per standard of care (if not already available).

At the time of surgery, local anesthesia will be administered. Conscious sedation will be administered according to patient need and investigator preference, per standard care. Buccal and lingual flaps will be minimally reflected to a point up to 3mm apical to the bony crest.

Prior to tooth extraction, the clinical measuring stent will be placed and measurements of ridge width and ridge height will be taken and recorded to the nearest 0.5mm. Ridge width will be measured to the nearest 0.5mm using a ridge caliper at a point approximately 4mm apical to the facial and lingual bony crest through small holes created in the stent at those locations. Ridge height will be measured to the nearest 0.5mm through two holes in the occlusal aspect of the stent – one hole directly above the facial bony crest and another hole directly above the lingual bony crest. This stent will be retained for use during the subsequent implant placement surgery.

Tooth extraction will be performed as atraumatically as possible. Following tooth extraction, a final determination of enrollment into the study will be conducted based on the integrity of the buccal bone wall plate at the extraction site. If the buccal plate is intact, defined as no bony dehiscence greater than 50% of the socket depth, the patient will remain enrolled in the study.

Conversely, if the buccal plate integrity has not been maintained (bony dehiscence >50%) the patient will be exited from the study and standard care therapy will be delivered to the patient.

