Approximately 16 weeks (\pm 2 weeks) after the extraction, implant surgery will be performed (standard of care). The width of keratinized tissue will be measured at the prospective implant site. A piece of floss will be run over the keratinized tissue and cut to the width of keratinized tissue, i.e. from the mucogingival junction (MGJ) on the buccal to the MGJ on the lingual. The floss will be then measured with a ruler to the closest 0.5mm.

After local anesthesia (and conscious sedation if requested), the patient will undergo implant placement surgery at the previously extracted tooth site and if required simultaneous guided bone regeneration (GBR) will be performed as per standard care. First, the individual subject's measuring stent and caliper will be used to determine the ridge width and ridge height at the same locations as done in the tooth extraction/grafting surgery visit. During the implant bed preparation, a hollow drill will be used to allow retrieval of a bone core which will be collected and stored in formalin and subsequently examined histologically and outcomes including percentages of new bone formation, residual graft and connective tissue/other will be recorded.

- During the implant placement procedure, the following data will be recorded per standard care:
- Bone quality according Lekholm and Zarb (1985) classification
- Absence/Presence of bone defect, including dehiscence or crater like defect. If present, at what site(s) (Buccal, Mesial, Lingual, Distal) and what are the respective depth and width of these defects.
- Absence/Presence of bone fenestration. If present what is the size of the fenestration in height and width.
- Was additional bone grafting needed in case of thin bone or dehiscence of threads? Yes/No

Subject participation ends at the time of implant placement. However, standard care post-operative visits will be provided after implant placement. Generally, one or two post-operative visits will be provided during the first month after implant surgery to insure adequate healing.

9. Preparation/Handling/ Storage/Accountability of Investigational Drug, Biologic, or Device

N/A - This study does not include any investigational products (e.g. drugs, devices or biologics)

N/A - An Investigator Brochure is attached

N/A - A Drug/Device Manual is attached

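### The ridge-change comparisons ignore the baseline measurement already taken; a baseline-adjusted model would remove the effect of chance imbalance and usually gain precision

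*Combined protocol and SAP*

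**What the plan says.** Section 8.8 lists the secondary outcomes as "change in ridge width; change in buccal ridge height, and change in lingual ridge height". Each has a genuine baseline. At Visit 2, before extraction and with the stent in place, "measurements of ridge width and ridge height will be taken and recorded to the nearest 0.5mm". At Visit 5 the subject's own "measuring stent and caliper will be used to determine the ridge width and ridge height at the same locations".

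Section 12.4 covers histologic and clinical parameters together: "The significance of variation in the mean with group BioOss collagen or Ossix Bone will be assessed with two-sample" t-tests, two-sided at 5%. It names no covariate. The only linear model in the plan serves another purpose: "The significance of variation in the group effect with another variable will be assessed with an interaction term in a linear model". That asks whether the graft effect differs across levels of an unnamed factor. It is not a baseline-adjusted comparison of the grafts.

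On allocation, section 8.8 says: "The patient will be assigned to either group by simple randomization with a 1:1 ratio". Section 10.1 implements this with 22 shuffled envelopes per arm. Neither section stratifies by ridge size or tooth type. Section 12.2 requires 14 compliant patients per arm and enrols 22.

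**The concern.** Subtracting the baseline is one way of adjusting for it, but it imposes a slope of exactly 1. If follow-up rises by less than 1 mm for each extra millimetre at baseline, subtraction over-corrects. The arm that happens to start with larger ridges then appears to lose more. Averaged over all randomizations this cancels, so the test keeps its validity. In the single trial that is run, it does not cancel.

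This trial is open to such imbalance. It is small and allocation is unstratified. Eligible teeth run from incisors to premolars, so baseline dimensions can plausibly vary. The analysis set is those who complete (section 12.3), so the envelopes do not guarantee balance among the patients analysed.

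At stake are the estimate and confidence interval for hypothesis (b) in section 12.1, on ridge dimensions. If adjustment is not prespecified, there is also a temptation to choose between adjusted and unadjusted results once an imbalance has been seen.

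**Working it through.** **The plan's own figure.** There is none for the ridge outcomes. Section 12.2 is sized to "detect a mean difference in percentage of new bone formation of 1 SD", by Mann-Whitney test, with 88.5% power at 14 per arm. With 14 per arm, 1 SD and a two-sided 5% level, a t-test gives 72.1% and a Mann-Whitney test on normal data about 68% by simulation, so 88.5% is not reproduced on those assumptions. That is a separate matter, and nothing below depends on it.

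**Inputs from the documents.** n = 14 per arm evaluable, 22 per arm if nobody is lost; two-sided 5%.

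**Inputs assumed.** Baseline SD 1, follow-up SD k, correlation r, so the true slope is rk. The documents give neither r nor k.

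**Formulas.**
- Variance of a change score: 1 + k² − 2rk, with 2n − 2 degrees of freedom.
- Effective variance after adjustment: k²(1 − r²) × [1 + 1/(2n − 4)], with 2n − 3 degrees of freedom. The bracket is the cost of estimating the slope: 25/24 = 1.042 at n = 14 and 1.025 at n = 22.
- Shift in the change-score estimate: (1 − rk) × baseline imbalance, in the opposite direction to the imbalance.

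**Precision with equal SDs (k = 1).** The variance ratio reduces to (1 + r)/2 × bracket. For example, at r = 0.5 and n = 14 it is 0.75 × 1.042 = 0.78. Power is for an illustrative difference of 1 SD of change, which the plan does not state for any ridge outcome.

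| r | Variance ratio, adjusted / change (n = 14) | Power adjusted, n = 14 (unadjusted 0.72) | Power adjusted, n = 22 (unadjusted 0.90) |
|---|---|---|---|
| 0.3 | 0.68 | 0.87 | 0.98 |
| 0.5 | 0.78 | 0.82 | 0.96 |
| 0.7 | 0.89 | 0.77 | 0.93 |
| 0.8 | 0.94 | 0.75 | 0.92 |
| 0.9 | 0.99 | 0.72 | 0.91 |
| 0.95 | 1.02 | 0.71 | 0.90 |

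Simulation at n = 14 (20,000 runs per setting) gave power of 0.874, 0.818, 0.773, 0.747, 0.726 and 0.710, in agreement. Break-even is where (1 + r)/2 × bracket = 1: r = 0.92 at n = 14 and r = 0.95 at n = 22.

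**Unequal SDs (n = 14).** At r = 0.7 the ratio is 0.65 for k = 0.8, 0.89 for k = 1.0 and 1.01 for k = 1.2.

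**Worst case for adjustment.** If rk = 1, subtraction is already optimal. The ratio is then 25/24 = 1.04, and power is 0.70 against 0.72.

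**Imbalance.** The chance that the arms differ at baseline by more than 0.5 SD is 2 × [1 − Φ(0.5 × √(n/2))], which is 0.186 at n = 14 and 0.097 at n = 22. With equal SDs, a 0.5 SD imbalance shifts the estimate by 0.25, 0.10 and 0.05 baseline SD at r = 0.5, 0.8 and 0.9. In simulation the slope of the change-score estimate on the imbalance was −0.50, −0.31 and −0.10 at r = 0.5, 0.7 and 0.9. For the adjusted estimate it was about 0.

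**The case against.** The strongest reply is that the plan contains no error. The endpoint is change, the test compares mean change, and randomization makes that comparison valid. This stands: the point concerns efficiency and chance imbalance, not validity.

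Second, the gain depends on assumptions. Equal SDs force the slope below 1. If follow-up SD exceeds baseline SD by 10%, the variance ratio at 14 per arm is 0.96, 1.01 and 1.04 at r = 0.7, 0.8 and 0.9; at 20% it is 1.01, 1.04 and 1.02. This also stands. Yet at r = 0.5 a gain remains (0.85 and 0.91), and a smaller follow-up SD makes it larger (0.67 at SD ratio 0.8 and r = 0.8).

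Third, height is read through the occlusal holes of a subject-specific stent that is reused at implant surgery. Both readings share an offset, which pushes the slope towards 1, and subtraction removes it. For the two height outcomes the precision gain may therefore be near zero; width is the better case.

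Fourth, the t-test's standard error already allows for chance imbalance, and the conditional shift is modest. With equal SDs at 14 per arm, a 0.5 SD imbalance moves the estimate by 0.66, 0.42 and 0.30 of a standard error at r = 0.5, 0.8 and 0.9. That is correct, but adjustment removes the shift.

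Finally, only secondary outcomes are affected, 1 SD of change is not a planned effect, and the 22-per-arm figures assume no losses although 30% dropout is expected. All of this is so, and it limits the weight of the point.

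**Conclusion.** The concern holds as an improvement that should be made; it does not expose an invalid test. The baseline is collected, but it enters the group comparison only with a slope fixed at 1.

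At 14 per arm with equal SDs, the effect of adjustment runs from 32% less variance (r = 0.3) to 2% more (r = 0.95). The trade is asymmetric. At r = 0.5 the illustrative power rises by about 10 points, from 0.72 to 0.82; in the worst case about 2 points are lost. The word *usually* is warranted because adjustment loses only when the true slope is close to 1, and then by at most 4% in variance at 14 per arm.

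The size rests on assumed correlations and SD ratios, so confidence in it is medium. The primary histologic outcomes and the sample size are untouched.

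**What to change.** In section 12.4, state that each ridge outcome (width, buccal height, lingual height) will be analysed with a linear model containing group and the baseline value of the same dimension. Report the adjusted mean difference with its 95% confidence interval. Keep the unadjusted t-test on change as a sensitivity analysis.

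This costs one sentence and no new data. It uses one degree of freedom per model. At 14 per arm that means about 1 point of power if r is about 0.95 with equal SDs, and at most about 2 points if the true slope is exactly 1. The sentence should be added before outcome data are examined, so that adjustment cannot depend on the imbalance observed.

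### Section 12.4 plans clinical–histologic correlations with no term for treatment arm; if the arms are pooled and the graft affects both measures, material difference and patient-level association are mixed

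*Combined protocol and SAP*

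**What the plan says.** Section 12.4 (Statistical Analyses) gives these correlations one sentence: "Spearman rank and Pearson correlations between clinical parameters and histologic parameters will be analyzed as well". It names no pairs, no null hypothesis and no lead coefficient, and it does not mention treatment arm. Shortly before, the section sets a general rule: "All statistical testing will be two-sided with a significance level of 5" percent.

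The section does plan one model containing a group effect: "The significance of variation in the group effect with another variable will be assessed with an interaction term in a linear model". The other variable is not named, and the model is not linked to the correlations.

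Section 8.8 lists the measures. The histologic outcomes are three tissue percentages ("vital bone formation, % residual graft material, and" connective tissue/other). The ridge outcomes are "change in ridge width; change in buccal ridge height, and change in lingual ridge height". Section 12.1 states nulls for arm differences on both sets, the second being "b.) No dimensional differences in alveolar ridge after ridge preservation with BioOss Collagen or Ossix Bone". It states no hypothesis about correlation.

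**The concern.** The trial compares two graft materials on tissue composition and on ridge change. If one material does better on both, the arms form two separated clouds of points. A coefficient computed over all subjects is then non-zero even when histology tells nothing about ridge change among patients given the same material.

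The documents themselves make this plausible. The dog study cited in Sections 2 and 4 favoured the test material on vital bone and on ridge restoration.

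At stake is how a secondary result is read. A report that more vital bone goes with less ridge loss would be taken as a relationship between patients, when it might only restate that one material scored better on both. The reverse can also happen: arm effects in opposite directions can hide a within-arm association that exists.

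**Working it through.** **Inputs from the documents.** Two arms, 1:1 (Section 10.1). Section 12.2 says a "sample size of 14 patients per group was enough to detect a mean difference in percentage of new bone formation of 1 SD", with 22 per group enrolled. Tests are two-sided at 5% (Section 12.4). Three histologic by three ridge measures make 9 pairs; with two coefficients, 18 tests.

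**Assumed.** Ridge effects of 0 to 1.5 SD, since no ridge effect size is given. The only histologic effect size is the 1 SD for new bone; 0, 0.5 and 1.5 SD are added to show the range. Data are normal with unit within-arm SD.

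**The plan's own figures.** The only figure that governs the correlations is the 5% level. With no arm effects, simulation reproduces it: 4.9% (Pearson) and 5.1% (Spearman). Section 12.2 also states power "by Mann-Whitney U test at the 0.05 level with a power of 88.5" percent. That is not reproduced from its stated inputs: two-sided Mann-Whitney power at 14 per group and 1 SD is 70.3% for normal data. This is a separate matter; only the group sizes and the 1 SD are used here.

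**Correlation created by arm effects alone.** Let d1 and d2 be the arm differences in within-arm SDs. With equal arms and zero within-arm correlation, the between-arm part adds d1·d2/4 to the covariance and d²/4 to each variance:

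r = (d1·d2/4) / √[(1 + d1²/4)(1 + d2²/4)]

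- 0.5 and 0.5 SD: 0.0625/1.0625 = 0.06
- 1 and 0.5 SD: 0.125/√(1.25 × 1.0625) = 0.11
- 1 and 1 SD: 0.25/1.25 = 0.20
- 1.5 and 1.5 SD: 0.5625/1.5625 = 0.36

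**Rejection rates at a nominal 5%, zero within-arm correlation** (40,000 simulated trials per row; Pearson/Spearman):

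| Effects (SD) | Pooled, 14 per arm | Pooled, 22 per arm |
|---|---|---|
| 0 and 0 | 4.9 / 5.1% | 5.0 / 5.0% |
| 1 and 0 | 4.9 / 5.1% | 5.0 / 5.0% |
| 0.5 and 0.5 | 6.2 / 6.1% | 6.7 / 6.7% |
| 1 and 0.5 | 8.7 / 8.4% | 11.0 / 11.0% |
| 1 and 1 | 18.0 / 18.3% | 26.3 / 26.9% |
| 1.5 and 1.5 | 50.6 / 53.4% | 71.6 / 74.4% |

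With adjustment for arm, the rate lies between 4.8% and 5.2% in every row, for both coefficients and both sample sizes. Better retention makes the pooled problem larger.

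**Masking.** With within-arm r = 0.5 and effects of +1 and −1 SD, the pooled correlation is (0.5 − 0.25)/1.25 = 0.20. At 14 per arm the pooled Pearson test then has about 14% power, against about 78% adjusted for arm.

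**Two coefficients.** Counting a pair as positive if either test is significant gives 6.5% with no arm effects, because Pearson and Spearman on the same data are strongly dependent.

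**The case against.** The strongest reply is that the plan never says the arms will be pooled. Correlations run within each arm would satisfy the sentence and would have no such problem. That stands: what is shown is under-specification whose literal reading is pooled, not a commitment to a faulty analysis. Silence still leaves the choice open until the data have been seen.

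A reader might infer several stronger things that the documents do not support:

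- **That any graft effect breaks the 5% level.** It takes an effect on both measures of a pair. With an effect on only one, the rate stays near 5%; at 0.5 SD on both it is 6 to 7%.
- **That 1 SD on both is the design effect.** Section 12.2 gives 1 SD for new bone only, and the dog study is cited without an effect size.
- **That the pooled test is invalid.** It remains an approximately valid test of zero overall correlation. It fails as a test of within-arm association, and the plan states neither null.
- **That a graft-driven correlation is not biological.** A material that changes both bone and ridge produces a real relationship between materials. It is just not a patient-level association within a material.
- **That Pearson must be dropped.** The second coefficient adds little error; naming one as main is enough.

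The correlations also serve no objective in Section 3 and no hypothesis in Section 12.1, so the harm is confined to an ancillary result. The linear model in Section 12.4 shows that adjustment for group is within the plan's reach, but it is not applied to the correlations.

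**Conclusion.** The point holds as a gap in specification. Section 12.4 names plain coefficients and nothing ties them to arm. On the pooled reading, the false-positive rate for within-arm association runs from about 5% (one measure affected) through 6%, 9% and 18% to just over 50% (1.5 SD on both) at 14 per arm. With 1 SD on both it is 26% at 22 per arm. These figures rest on normal data, equal arms, zero within-arm correlation and assumed ridge effects. How far the level is off in this trial cannot be known from the documents. The comparisons of the two materials are untouched. The change is still worth making: it is cheap, and it decides whether a reported correlation can be read as a relationship between patients.

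**What to change.** Replace the correlation sentence in Section 12.4 with wording such as: *Associations between clinical and histologic parameters will be estimated by the partial Spearman correlation adjusted for treatment group (main), with the partial Pearson correlation as a supporting value. Within-arm coefficients and 95% confidence intervals will be shown. These analyses are exploratory.* Pearson could equally be the main coefficient, provided one is named in advance.

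The cost is one sentence and one degree of freedom per correlation (at 14 per arm, 25 instead of 26). No new data or additional patients are needed. Within-arm intervals will be wide at 14 to 22 patients, which is one more reason for the exploratory label.
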